### 13.7 Follow-up for final outcome of adverse events

During the trial, the investigator should follow up for final outcome on all AEs (including SAEs). Once a subject leaves the clinical trial, the investigator should follow up on the outcome of all non-serious AEs classified as of possible/probable relationship to the IMP for 14 days or until the final outcome is determined, whichever comes first. SAEs must be followed up until a final outcome has been established, that is, the follow-up may continue beyond the end of the clinical trial. For SAEs which have stabilised and from which the subject cannot be expected to recover during the trial or the safety follow-up periods, for example chronic or stabilised conditions, the final outcome should be reported as 'not recovered'. In addition, a statement that the SAE has stabilised or is chronic should be added to the narrative description of the SAE on the SAE form.

### 13.8 Handling of an urgent safety measure

An urgent safety measure is a measure taken to implement an action/protocol deviation under an emergency. This is defined as “...the occurrence of any new event relating to the conduct of the trial or the development of the investigational medicinal product where that new event is likely to affect the safety of the subjects, the sponsor and the investigator shall take appropriate urgent safety measures to protect the subjects against any immediate hazard.” (31).

If the investigator becomes aware of information that necessitates an immediate change in the clinical trial procedure or a temporary halt to the clinical trial in order to protect clinical trial subjects from any immediate hazard to their health and safety, the investigator can do so without prior approval from LEO, regulatory authorities, or IRBs/IECs.

The investigator must immediately inform LEO – by contacting the clinical project manager or medical expert – of this change in the clinical trial procedure or of the temporary halt providing full details of the information and the decision making process leading to the implementation of the urgent safety measure.

LEO must act immediately upon receipt of the urgent safety measure notification in accordance with internal procedures and local legislation.

## 14 Statistical methods

### 14.1 Sample size

This trial aims to achieve a total of 36 subjects completing the trial according to the protocol. Assuming a drop-out rate of 20%, a total of 45 subjects will be randomised. The screening failure rate is expected to be approximately 20%.

With 36 subjects completing the trial, a within-subject comparison of lesion-specific IGA scores according to the primary endpoint will detect a treatment difference with at least 90% power, assuming a probability of clearance of 5% for vehicle and 35% for delgocitinib cream. The power calculation is based on a Wald contrast test for equality of clearance probabilities evaluated at a 5% significance level.

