### Overall rationale for the amendment

The protocol is amended to address recruitment issues. DLE is a rare disease, and the number of patients eligible for this trial is very limited. The exclusion criteria concerning tobacco use and hepatitis B serology have been modified to ease recruitment without compromising the safety of the subjects and the evaluation of trial results.

Subjects who are in screening when this amendment is approved will be re-assessed for eligibility according to the amended eligibility criteria.

All changes to the protocol are summarised below.

| Section no. and name   | Description of change  | Brief rationale  |
|--|--|--|
| 8.3
Exclusion criteria
(also protocol synopsis and Appendix 4) | Exclusion criterion no. 17 was changed from a pre-defined limit (>70 cigarettes/week or >70 g tobacco/week) to instead exclude subjects with unstable or fluctuating use of tobacco.   | To allow randomisation of subjects smoking >10 cigarettes/day. Tobacco may affect the course of DLE and thus the trial results, but as long as the tobacco use is stable for at least 1 month prior to screening, the actual consumption is considered less important.   |
|  | Exclusion criterion no. 26 was modified to only exclude positive human immunodeficiency virus antibody, hepatitis B surface antigen, and hepatitis C virus antibody serology (and not positive hepatitis B surface antibody and hepatitis B core antibody serology). | Reactivation of hepatitis B is considered only a theoretical risk, as the treatment is topical and only applied to a very small area ( $\leq 1\%$ of BSA), and therefore the systemic exposure is negligible. Furthermore, subjects will not be randomised if they have signs of active infection, and randomised subjects will be monitored for signs of active infection during the trial. |
| Section 11.5.2
Non-invasive skin sampling                         | It was added that non-invasive skin sampling will not be done for subjects who have plaster or bandage allergy.  | To avoid allergic reactions to the adhesive patches used for non-invasive skin sampling.   |
| Appendix 9
Protocol amendment history                             | New appendix added containing the summary of the previous protocol amendment.  | To document the protocol amendment history, and to keep only the most recent amendment summary at the start of the protocol.   |

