| Investigational medicinal products | 
 
• Name of IMP: delgocitinib cream.
 
• Active substance: delgocitinib.
 
• Formulation: cream.
 
• Formulation strength: 20 mg/g and vehicle.
 
• Dose and method of administration: topical application twice daily.
 
   |

|  |   |
|--|---|
| Duration of treatment                  | 6 weeks.  |
| Number of subjects                     | This trial aims to have 36 subjects evaluable for the primary endpoint. Assuming a drop-out rate of 20%, approximately 45 subjects will be randomised to achieve this.  |
| Number and distribution of trial sites | Approximately 20 sites in several countries in the EU and/or United States.   |
| Statistical methods                    | 
Primary endpoint:
 
The efficacy of delgocitinib cream compared with vehicle will be analysed in a within-subject comparison of lesion-specific treatment success (defined as an IGA score of 0 or 1 at Week 6) using McNemar's test.
 
Secondary endpoints:
 
Within-subject comparisons of the numbers of AEs, subjects with AEs, and treatment-related, lesion-specific AEs will be done by treatment using a Wilcoxon signed rank test.
 
Within-subject comparisons of lesion-specific binary endpoints to assess treatment difference at Week 6 will be done by McNemar's test.
 
Within-subject comparisons of lesion-specific disease activity scores to assess treatment difference at Week 6 will be done by a Wilcoxon signed rank test.
 
The analysis of the primary and secondary endpoints will be performed on the per protocol analysis set and repeated for the full analysis set as a sensitivity analysis.
 |
| Signatory investigator                 | [name], Univ. [name]. Med.
Department of Dermatology, Venereology and Allergology, Campus Charité Mitte, Berlin, Germany  |
| Sponsor                                | LEO Pharma A/S, [name].   |

[figure not shown]

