#### 5.4 Ethical considerations

This trial will be conducted in accordance with the ethical principles that have their origins in the Declaration of Helsinki and the International Council for Harmonisation (ICH) Good Clinical Practice (GCP) guidelines, and in compliance with the approved protocol and applicable regulatory requirements.

No children, adolescents, or other vulnerable subjects incapable of giving informed consent will be enrolled in this clinical trial. Furthermore, women who are pregnant, breastfeeding, or trying to become pregnant will not be enrolled in this clinical trial. Women of childbearing potential must agree to use a highly effective method of contraception to prevent pregnancy during the clinical trial. In addition, all female subjects of childbearing potential will have a pregnancy test performed before and during the trial, and at end of treatment and safety follow-up to ensure that no foetuses are exposed to the IMP. No contraceptive measures are required for male subjects exposed to delgocitinib cream as no or negligible systemic absorption is expected.

Eligible subjects with 2 active DLE lesions (target lesions) will be randomised to treatment with delgocitinib cream 20 mg/g and vehicle to each of the target lesions. Thus, all trial subjects will receive active treatment on 1 DLE lesion twice daily for 6 weeks. This treatment duration is expected to be sufficient to induce significant improvement in the disease activity. The choice of a vehicle control and the within-subject trial design is considered appropriate for addressing the objectives of this trial. Based on evidence from a previous within-subject trial in a similar patient population, there are no concerns that vehicle treatment of 1 target lesion for the duration of the trial will cause permanent skin damage from DLE (21). For the same reason, it is also considered ethically justified to prohibit other topical DLE treatments during the treatment phase to avoid accidental use of these on the target lesions. The

within-subject trial design reduces the required sample size by eliminating the between-subject variation. Reducing the required number of subjects is considered very important for recruitment due to the low number of eligible patients with this rare disease.

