### **11.2.8 Identification of target lesions**

The investigator will identify 2 comparable DLE lesions which are less than 6 months old and have clinical signs of disease activity according to the eligibility criteria. There is no lower limit for size of the target lesions as long as they are considered large enough for complete clinical evaluation. The maximum expected lesion size is 15 cm in diameter corresponding to 1% of BSA (1). The size of each target lesion will also be recorded (see Section 11.6.2).

The 2 target lesions should preferably be located in the same anatomical region, but priority should be given to the similarity in clinical appearance of disease activity signs. If there are more than 2 lesions amenable for clinical evaluation, the investigator will select the 2 lesions which are most suitable as target lesions. Lesions on the scalp may also be included if they fulfil the eligibility criteria.

The investigator will identify and evaluate 2 potential target lesions at screening and will assess these again at baseline to make sure that both target lesions meet the necessary requirements. In the unlikely event that a potential target lesion selected at screening no longer meets all eligibility criteria at baseline, the investigator has the option to select a new target lesion, if available. It will be documented in the source data and the eCRF whether the target lesions selected for randomisation at baseline are the same as the potential target lesions identified at screening (see also Section 9.3).

At baseline, the selected target lesions will be numbered (lesion 1 and 2) as described in Section 9.3, and the location of the target lesions will be recorded in the eCRF (scalp, forehead, temple, malar, cheek, eyebrow, lower eyelid, upper eyelid, lower lip, upper lip, chin, external ear, external nose, neck, trunk, arm, or leg). The location of the lesions will be specified in more detail in the subject records to ensure correct identification of the lesions at subsequent visits.

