#### **14.3.4 Analysis of primary endpoint**

The efficacy of delgocitinib cream compared with vehicle will be analysed in a within-subject comparison of lesion-specific treatment success (defined as an IGA score of 0 or 1 at Week 6) using McNemar's test.

The PP analysis set will be the primary analysis set for the primary endpoint. The analysis will be repeated on the FAS as a sensitivity analysis.

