**Risk assessment**

In this trial, the risks to critical trial processes and data have been evaluated. The main risk is recruitment problems, as DLE is a rare disease. This risk will be addressed by thorough feasibility analysis during the trial planning phase.

Other identified risks are:

- Inconsistency within the primary endpoint data due to IGA inter-rater variability.
- Accidental investigator unblinding due to slight differences in colour between the 2 IMPs.
- Accidental use of the wrong IMP on 1 or both target lesions.

Risk mitigation activities to ensure data quality and subject safety include:

- To ensure consistent efficacy assessments (IGA), all assessors will receive training before starting the trial. Whenever possible, the efficacy assessments will be made by the same investigator at each visit for a given subject to reduce inter-rater variability.
- To avoid unblinding, sites will be required to assign a staff member who is not involved in clinical assessments to apply the first IMP doses at the baseline visit.

- To ensure that the subjects apply the IMPs to the correct lesions throughout the trial, the subjects will receive a body diagram illustrating the location and assigned treatment of each target lesion at the baseline visit as a reference/reminder.

In addition, to ensure consistent AE monitoring and avoid duplicate AE reports, CRO staff conducting the exit interviews will be properly trained to detect and report any AEs that might be reported during these interviews (Section 13.2).

Throughout the trial, regular data quality review meetings will be held to ensure continuous improvement of data quality and prevention of mistakes. During monitoring visits at the trial sites, the CRAs will verify that investigators work according to the protocol.

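### Does the 90% power claim fail because Section 14.1 powers a Wald test while the planned primary test is McNemar's, with no version named?

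*Combined protocol and SAP*

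**What the plan says.** Section 14.1 states that the primary comparison in 36 completers "will detect a treatment difference with at least 90% power, assuming a probability of clearance of 5% for vehicle and 35% for delgocitinib cream". It then names the test behind that figure: "The power calculation is based on a Wald contrast test for equality of clearance probabilities evaluated at a 5% significance level". With 20% drop-out, 45 subjects are to be randomised.

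Section 14.3.4 plans a "within-subject comparison of lesion-specific treatment success (defined as an IGA score of 0 or 1 at Week 6) using McNemar's test", and the synopsis says the same: "lesion-specific treatment success (defined as an IGA score of 0 or 1 at Week 6) using McNemar's test". Neither names a version. No section gives a within-subject correlation or an expected proportion of discordant pairs.

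Section 14.3.11 sets two-sided 5% tests, says they are to be read descriptively, and leaves the statistical analysis plan to be finalised before the randomisation code is broken.

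**The concern.** The power statement names one test and the analysis section another, and the second comes in versions that differ in power when discordant pairs are few. About 13 are expected here. If the analysts ran the exact or the continuity-corrected version and the lesions were independent, power would be about 87%, below the stated 90%.

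The choice can also decide a result. With 11 discordant pairs favouring delgocitinib and 3 favouring vehicle, p is 0.033 uncorrected and 0.035 mid-p, but 0.057 exact and 0.061 continuity-corrected. An unnamed version therefore leaves some discretion.

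Power also looks worth protecting. Section 5.4 says "Reducing the required number of subjects is considered very important for recruitment due to the low number of eligible patients with this rare disease", Appendix 3D says "The main risk is recruitment problems, as DLE is a rare disease", and Amendment 2 explains that "The protocol is amended to address recruitment issues".

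**Working it through.** **Inputs from the documents.** n = 36 pairs, success rates 0.35 and 0.05, drop-out 20% (Section 14.1); two-sided 5% (Section 14.3.11).

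**Assumed.** The within-subject correlation rho is not documented. With these success rates it can lie only between about -0.17 and +0.31.

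**Cell probabilities.**
- p11 = 0.35 × 0.05 + rho × √(0.35 × 0.65 × 0.05 × 0.95) = 0.0175 + 0.1040 × rho
- p10 = 0.35 - p11 and p01 = 0.05 - p11
- At rho = 0: p10 = 0.3325, p01 = 0.0325, discordance 0.365, so 36 × 0.365 = 13.1 discordant pairs are expected.

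**Step 1: the plan's own figure.** Take the Wald test on the difference in probabilities:
- SE = √((0.365 - 0.30²)/36) = √(0.275/36) = 0.0874
- 0.30/0.0874 = 3.43; 3.43 - 1.96 = 1.47; power = 93.0% (94.5% by enumeration)
- At the most negative possible correlation: 89.9% by normal approximation, 90.6% by enumeration.
- 36/(1 - 0.20) = 45.

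Both stated figures reproduce. Section 14.1 does not define the Wald construction, and the scale matters: an unpaired contrast of log-odds would give 79%. Since the text speaks of equality of probabilities and the difference scale returns its figure, that is the natural reading.

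**Step 2: the planned test.** The number of discordant pairs is Binomial(36, p10 + p01), split binomially with probability p10/(p10 + p01). Power is the summed probability of all outcomes with p ≤ 0.05.

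| rho (assumed) | Uncorrected | Mid-p | Exact | Continuity-corrected |
|---|---|---|---|---|
| -0.17 (lowest possible) | 87.2% | 87.1% | 81.3% | 80.4% |
| 0 | 91.6% | 91.5% | 86.8% | 86.5% |
| 0.10 | 94.3% | 94.2% | 90.3% | 90.3% |
| 0.20 | 97.0% | 96.8% | 93.9% | 93.9% |
| 0.30 | 99.5% | 99.1% | 97.4% | 97.4% |

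Power reaches 90% at rho of about -0.06 for uncorrected and mid-p, and at about 0.09 for exact and continuity-corrected.

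**Step 3: what naming mid-p would buy over the uncorrected test.**
- Up to 36 pairs, the two decide differently at only four discordant splits: 4/0, 15/6, 18/8 and 21/10. In each, the uncorrected test rejects and mid-p does not.
- Largest type I error at 36 pairs, for discordance up to one half: uncorrected 5.1%, mid-p 4.7%, exact 3.0%, continuity-corrected 2.5%.
- One half is the ceiling when the two rates are equal and rho is not negative, since discordance is then 2p(1 - p)(1 - rho) ≤ 0.5.

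**Step 4: pairs needed for 90% at rho = 0.** Uncorrected and mid-p need 35 (mid-p gives 89.7% at 34 and 90.7% at 35). Exact needs 40 (89.9% at 39, 90.9% at 40). With 20% drop-out this is 35/0.8 = 43.75, so 44 randomised, against 40/0.8 = 50. The plan randomises 45.

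**The case for a change.** The strongest case for acting is that the power statement does not describe the test that will be run, that the documents rule out neither the exact nor the continuity-corrected version, and that settling this costs a few words. The per-protocol set is primary and can shrink at blind review (Section 14.2), so fewer than 36 pairs is possible. At an assumed 30 pairs and independence, mid-p gives 85.1% and exact 77.7%. Naming the version before unblinding would also remove the discretion shown by the 11-to-3 example.

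Much of this stands as fact: the test names differ, the version is open, and fixing it in advance is good practice. The rest carries less weight:

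- The recruitment passages do not bear on the McNemar version. Section 5.4 argues for the within-subject design, and the amendment concerns tobacco and hepatitis B criteria. Since 36 and 45 would not change, the 44-versus-50 comparison saves nobody.
- Mid-p does not guarantee 90% either. It falls short at 34 pairs under independence, or at 36 pairs with a correlation below about -0.06.
- Mid-p against exact is a genuine trade-off: the exact test guarantees its level and mid-p does not.
- The design makes positive correlation plausible. Section 11.2.8 says "The investigator will identify 2 comparable DLE lesions which are less than 6 months old" and prefers the same anatomical region. The size is undocumented, but about 0.09 brings every version to 90%.
- McNemar's test is also planned in Sections 14.3.5, 14.3.6.1, 14.3.8 and 14.3.9.1. Editing the primary endpoint alone would leave the other uses unspecified, so the natural place is one line in the statistical analysis plan covering all of them.

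**Conclusion.** No change to the plan is needed. The stated 90% is not shown to be wrong. It reproduces for a Wald test on the difference in probabilities, and it holds for McNemar's test in the usual unqualified sense: 91.6% at 36 pairs under independence, more with positive correlation. The gap of 3.2 to 3.5 points below 90% arises only with the exact or the continuity-corrected version and a correlation below about 0.09. Against the uncorrected reading, mid-p gains no power and about 0.4 percentage points in maximum type I error, which matters little when all tests are interpreted descriptively.

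What is left is a detail that the analysts would settle when they finalise the statistical analysis plan before unblinding. If they prefer the exact or the continuity-corrected version, the figure to bear in mind is about 87% under independence.

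This conclusion rests on the protocol's rates of 5% and 35%, on about 36 evaluable pairs, and on a within-subject correlation that is not clearly negative. The documents do not state the last of these.

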### 14.2 Trial analysis sets

All subjects screened in the trial will be accounted for in the CTR.

All randomised subjects will be included in the full analysis set (FAS). Exclusions from the FAS can be considered in special cases as described in ICH E9, Section 5.2.1 (Full Analysis Set). If it is decided to exclude a randomised subject from the FAS, a justification addressing ICH E9 will be given.

A per protocol (PP) analysis set will be defined by excluding subjects from the FAS who fulfil any of the following criteria:

- Receive no treatment with the IMPs.
- Do not complete the trial up to and including the Week 6 visit.
- Fail to provide efficacy data at the Week 6 visit.
- Are known to have used the wrong IMP on 1 or both target lesions.
- Do not fulfil the disease-defining inclusion criteria (that is, inclusion criteria no. 3-6).

Further exclusion of subjects or subject data will be decided upon after a blind review of the data, reviewing all the remaining in- and exclusion criteria, but focusing on concomitant medication that may affect DLE and also considering compliance and violations of visit windows.

A safety analysis set will be defined as all subjects who received IMP.

The decisions regarding inclusion/exclusion of subjects or subject data from the trial analysis sets will be documented in the analysis set definition document before breaking the randomisation code.

### **14.3 Statistical analysis**

#### **14.3.1 Disposition of subjects**

The reasons for discontinuation of IMP or withdrawal from trial will be presented for all randomised subjects.

#### **14.3.2 Demographics and other baseline characteristics**

Descriptive statistics of demographics and other baseline characteristics will be presented for all randomised subjects by site. Lesion-specific baseline characteristics will be presented for all randomised subjects by site and treatment.

#### **14.3.3 Exposure and treatment compliance**

The duration of exposure to treatment will be calculated as the number of days from the date of first application of IMPs to the date of last application of IMPs, both days included. Exposure will be presented for the FAS as days of exposure.

Drug accountability data will be calculated by subtracting the weight of the used tubes from the mean normal weight of full tubes. Average total usage will be presented for each treatment for the entire treatment period.

Compliance with treatment regimen will be recorded in the eCRF. If any complications or deviations in administration are observed, these will be described as protocol deviations.

Treatment compliance will be presented for the safety analysis set for each treatment via the percentages of missed and/or excessive applications, and applications of wrong IMP.

